#### 12.2. Proportional Odds Assumption

The primary analysis model is based on an assumption of a proportional effect of treatment across the scale of the ordinal outcome. In order to assess the robustness of the results to this assumption, a dichotomous model is fit to every level of the ordinal outcome across the scale and the OR for each dichotomous break is presented. If the probabilities for the tails of the ordinal endpoint have small probabilities (<5%) they may not be conducted. No statistical test of proportional odds will be conducted.

#### 12.3. Analytic Approach for Secondary Dichotomous Endpoints

A Bayesian logistic regression model will be used for each dichotomous outcome. The model will always specify the “event” as the negative outcome and be parameterized so that an OR >1 implies benefit to patients. The model is the standard logistic link function model:

$$\log \left( \frac{\pi}{1 - \pi} \right) = \alpha - [factors]$$

References will be made to the factors in the model and their prior distribution. Many of these factors will be the same as the primary analysis model, with the same priors, as the parameters have similar interpretation. For example, all in-hospital mortality models should use the Beta prior distribution implied by the Dirichlet prior in the OSFD model. If not otherwise specified, the prior distribution for the main effect is  $\alpha \sim N(0, 1.82^2)$  (similar to a uniform prior on the probability scale).

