8.3 Model Priors

The treatment effects for arm a , within disease subtype s are modeled with the θ_s parameters. The β parameters model any covariate effects included in the model. The λ parameters model the effect of time within the pandemic.

The ordinal endpoint rates are modeled using an inverse Dirichlet model where the individual probabilities for the 23 outcomes are based on 1 patient's weight on equally likely outcomes.

$$\text{logit}(\alpha_{y,s}) \sim \text{Dirichlet}(1 * P), \text{where } P \propto 1$$

The site effects, $v_{Site,s}$, are modeled using a hierarchical model where site is nested within the country of the site:

$$v_{Site,s} \sim N(\mu_{country,s}, \tau_{country,s}^2), \text{site} = 2, \dots, N_{Site}$$

$$\mu_{country,s} \sim N(0,1); \tau_{country,s}^2 \sim IG(0.25,0.1), s = 1,2$$

A referent site, expected to be the largest enrolling site, will be set such that $v_{Site} \equiv 0$. The hyper-parameters of the site hierarchical model are separate by disease state s .

The effect of time (T) is modeled using a second-order normal dynamic linear model separately by disease state, s . The most recent two time periods are modeled as the referent time epochs with the time parameters set to 0. The preceding time epochs are modeled as a normal dynamic linear model as:

$$\lambda_1 = \lambda_2 \equiv 0$$

$$\lambda_3 \sim N(0,0.15^2)$$

$$\lambda_T - 2\lambda_{T-1} + \lambda_{T-2} \sim N(0, \tau_{Time}^2), T \geq 4$$

The treatment effect parameters are set against a control arm, which will be labeled in the arm-specific appendix. The treatment effect for the control arm, labeled as arm $a = 1$, will be set to 0 for each of the disease states:

$$\theta_{1,s} \equiv 0.$$

The effect of each treatment arm introduced will typically be modeled hierarchically across disease subtypes. The modeling of the treatment arms will be specified in appendices.

Any additional covariates included in the model will have independent $N(0,1)$ priors unless otherwise specified.

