Appendix 6: Additional data inclusion from other trials merged under ACTIV-4 platform

There are several clinical trials that have been testing safety and efficacy of Arm A and B regimens. Data collected in these trials will be included in the data analysis under this protocol provided that the subjects consented for the data to be shared or a waiver of consent and authorization had been granted by the reviewing IRB. The data will be labeled with subject ID and only include dates which are necessary to assess safety and efficacy endpoint events. All other private health information (PHI) will be removed. The data will be stored at the study coordinating center, University of Pittsburgh, in HIPAA compliant electronic system and only coordinating center staff will have access to the data. The statistical analysis plan will account for this additional data.

Appendix 7: Background and Rationale for Arm C: P2Y12 inhibitor for ICU Level of Care (Severe) Cohort

A7.1 Background and Rationale for Arm C

Analysis of therapeutic vs prophylactic dose anticoagulation in severely ill patients demonstrated that therapeutic dose anticoagulation was not superior, and there was a trend toward harm. Therefore prophylactic dose anticoagulation is considered standard of care for severely ill patients. The number of days with organ support or death over the first 21 days of the index hospitalization remained high despite standard of care treatment, and bleeding risk was < 2%. Therefore, additional antithrombotic and additional treatment strategies should be tested.

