#### 3.1. Reporting strategy

This SAP describes the planned analyses for the study. As outlined below, two cohorts (moderate illness, severe illness) may report at different times. Multiple reports describing the results of analysis may be prepared and published to ensure expedited dissemination of the study findings. It is anticipated that for each cohort, expedited, potentially preliminary reports will describe key primary and secondary findings and limited subgroup analyses.

Endpoints to be reported in these reports include:

- Organ support-free days to day 21 (primary endpoint)
- In-hospital mortality (key secondary endpoint)
- Major thrombotic events or death (key secondary endpoint)
- ISTH major bleeding (key safety endpoint)

Comprehensive reports providing complete characterization of trial results may subsequently be prepared and published.

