## 12. Analytic Approach

Each inferential analysis will be done using a Bayesian model. Some default frequentist methods are used for exploration and description. A summary of the analyses methods is provided below. Events that occur at low frequency will be reported descriptively and not modelled.

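### The default intercept prior for dichotomous endpoints, centred on a 50% event rate, tilts sparse harms such as major bleeding modestly towards P2Y12 if control is the reference arm

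*SAP*

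**What the plan says.** SAP 12.3 writes each dichotomous model as logit(π) = α − [factors], where the event is the bad outcome, and requires it to "be parameterized so that an OR >1 implies benefit to patients". On the intercept it says: "If not otherwise specified, the prior distribution for the main effect is" α ~ N(0, 1.82²), described as "similar to a uniform prior on the probability scale". In-hospital mortality is the only endpoint named with a different prior: it takes the Beta prior implied by the primary model. For the remaining terms, "Many of these factors will be the same as the primary analysis model, with the same priors".

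SAP 12.3 does not state how treatment is coded. Protocol 8.3 does, for the generic ordinal model: "The treatment effect for the control arm, labeled as arm" 1, is fixed at zero in each disease state.

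SAP 3.1 puts "ISTH major bleeding (key safety endpoint") among the endpoints for expedited reports, and SAP section 7 defines it as dichotomous. Protocol A7.1 says of the earlier severe cohort that "bleeding risk was < 2"%. SAP 12 adds: "Events that occur at low frequency will be reported descriptively and not modelled". It gives no count or rate that marks low frequency.

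**The concern.** A prior that is nearly flat on the probability scale looks harmless, and for one rate in isolation it is. With a reference-coded treatment effect it does not treat the arms alike. Control sits directly under a prior centred on 50%. P2Y12 sits at α − θ and can move away from that prior through θ. When the true rate is 1% to 3%, the prior pulls control up by more than P2Y12, and the gap appears in θ. Because OR > 1 means benefit, the gap always favours the drug.

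The endpoints most exposed are the harms: major bleeding, fatal bleeding, intracranial haemorrhage, heparin-induced thrombocytopenia and the single thrombotic events. Under SAP 12.13 major bleeding has no stopping boundary and is weighed by judgement. A published estimate that leans towards safety therefore matters even when it is far from any threshold.

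**Working it through.** **Inputs.** Intercept prior N(0, 1.82²) (SAP 12.3). Control as reference (Protocol 8.3; assumed to carry over). Treatment prior θ ~ N(0, 1) for a single cohort (SAP 12.1, item 13) or N(0, 10²) for cohort analyses (SAP 12.5). Equal allocation (Protocol 9.1.2). Assumption: 300 per arm, varied from 150 to 1,000.

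**The plan's own figure.** The logit of a Uniform(0,1) variable has SD π/√3 = 1.814, against the stated 1.82, so the description is accurate. On the rate scale the 95% prior range is logit⁻¹(±1.96 × 1.82) = 2.7% to 97.3%. For a 2% rate, logit(0.02) = −3.89 and −3.89/1.82 = −2.14, so the prior gives only 1.6% probability to a rate below 2%.

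**Model.** logit(p_control) = α; logit(p_P2Y12) = α − θ; OR = exp(θ).

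**Hand calculation, 6 of 300 in each arm.** Information on each arm's log-odds is 300 × 0.02 × 0.98 = 5.88. Prior precision is 1/1.82² = 0.302.

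- θ almost free (SD 10): α moves up by 0.302/(0.302 + 5.88) × 3.89 = 0.19. P2Y12 stays where its data put it, so OR = exp(0.19) = 1.21.
- θ ~ N(0, 1): the P2Y12 arm informs α with precision 1/(1/5.88 + 1) = 0.855. α moves by 0.302/(0.302 + 5.88 + 0.855) × 3.89 = 0.167, and θ = 0.167 × 5.88/(5.88 + 1) = 0.143. OR = exp(0.143) = 1.15.

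**Grid posterior** (median OR and P(benefit), 300 per arm):

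| Events, control v P2Y12 | Default, θ SD 1 | Default, θ SD 10 | ±1/2 coding, θ SD 1 / SD 10 |
|---|---|---|---|
| 3 v 3 | 1.28, 0.66 | 1.50, 0.70 | 1.00, 0.50 / same |
| 6 v 6 | 1.15, 0.61 | 1.21, 0.63 | 1.00, 0.50 / same |
| 10 v 10 | 1.09, 0.58 | 1.11, 0.59 | 1.00, 0.50 / same |
| 15 v 15 | 1.05, 0.56 | 1.06, 0.57 | 1.00, 0.50 / same |
| 2 v 3 | 1.08, 0.55 | 1.15, 0.57 | 0.82, 0.38 / 0.71, 0.34 |
| 3 v 6 | 0.78, 0.32 | 0.70, 0.29 | 0.64, 0.21 / 0.52, 0.16 |

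So with 3 v 6 events, P(harm) is 0.68 to 0.71 under the default, against 0.79 to 0.84 with symmetric coding. An intercept SD of 10 in place of 1.82 also brings 6 v 6 back to OR 1.00 to 1.01.

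**Sensitivity.** At 6 v 6, moving from 150 to 1,000 per arm takes the OR across about 1.13 to 1.27 and P(benefit) across 0.60 to 0.67. Adding 16 covariate indicators with N(0, 1) priors gives OR 1.17 (θ SD 1) and 1.23 (θ SD 10), so covariates alone do not remove the lean. If country and age priors widened the effective intercept SD to 2.6 (an assumption), 6 v 6 would give about 1.07 to 1.11.

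**Against the 99% threshold.** With at least one event per arm, the highest equal-count P(benefit) found was 0.865 (1 v 1, 1,000 per arm, θ SD 10). Only 0 v 0 comes close (0.976 to 0.985), and the low-frequency rule should keep that case out of the model.

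**The case against.** A reader might infer that equal bleeding counts would be declared a benefit of P2Y12. The documents do not support that. SAP 12.7 reserves a statistical claim for a posterior probability above 99% and always shows a 95% credible interval. At 6 v 6 with θ ~ N(0, 1) that interval is 0.44 to about 3.1, which nobody would read as benefit.

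A reader might also infer that DSMB decisions are distorted. That is not shown either. The safety table in SAP 12.13 lists raw counts, rates, differences and odds ratios with confidence intervals, and is not said to come from the SAP 12.3 model. Protocol 8.5.1 gives adverse-event monitoring its own prior, Beta(0.1, 0.9).

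Three further points limit the concern. The largest leans occur at 0 to 3 events per arm, where SAP 12 may leave the endpoint unmodelled. SAP 12.3 does not tie the prior to the control arm: α appears in both arms' equations, and the asymmetry follows only from a coding stated elsewhere. And the A7.1 bleeding figure is not labelled as ISTH major bleeding and does not describe patients on P2Y12.

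These points set the size of the problem but do not remove it. With no cut-off, nothing in the SAP settles whether its key safety endpoint at 6 to 10 events per arm is modelled or only described. If it is modelled, SAP 12.7 requires the tilted OR and its probability to be reported.

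**Conclusion.** The point holds as a modest bias in the estimate for sparse harms, always towards P2Y12, with a weakened harm signal. It is not a false claim of efficacy or safety. At 300 per arm the spurious OR is 1.15 to 1.21 at 6 events per arm, about 1.1 at 10 and about 1.05 at 15. A one-event excess on P2Y12 can change sign (2 v 3), and a doubling keeps its direction but is diluted (3 v 6).

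This rests on three assumptions: control-reference coding carries over from Protocol 8.3 to the dichotomous models; arms are between 150 and 1,000 patients; and the treatment prior lies between N(0, 1) and N(0, 10²). If the programmers already use symmetric coding, the lean at equal counts is zero and the SAP need only say so. The change is worth making before unblinding, but the trial's primary conclusion does not depend on it.

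**What to change.** In SAP 12.3, for dichotomous endpoints that use the default intercept prior:

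1. State the treatment coding, and use −1/2 for control and +1/2 for P2Y12. Equal counts in equal arms then give OR 1.00 and P(benefit) 0.50 at any event rate. Alternatively keep reference coding and widen the intercept prior, for example to SD 10.
2. In SAP 12 or 12.3, state the event count below which an endpoint is described and not modelled, and say on which side ISTH major bleeding is expected to fall.

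Leave in-hospital mortality on its Beta prior, which is deliberately matched to the primary model. Do not centre the intercept on the pooled event rate, because that would set the prior from the trial's own outcomes.

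The cost is a sentence or two and one line of code. Symmetric coding changes the meaning of the intercept, from the control log-odds to the midpoint of the arms. The wider prior lengthens the interval slightly: at 6 v 6 with θ ~ N(0, 1) it becomes 0.37 to 2.76, about 3% longer on the log scale than with symmetric coding (0.38 to 2.66). Common endpoints hardly change: at 60 v 60 of 300 the default lean is already only 0.302/(0.302 + 48) × 1.386 = 0.009 on the log scale, an OR of 1.01.

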#### 12.4. Analytic Approach for Secondary Time-To-Event Endpoints

All inferential time-to-event analyses will be done using a Bayesian piecewise exponential model. The Bayesian time-to-event model is intended to mirror a Cox proportional hazards model, with the underlying hazard rate modeled with a piecewise exponential model. The underlying hazard will be modeled with a hazard rate for each 10-day period in the model. The prior distribution for the hazard rate for each day is a gamma distribution with 1 day of

exposure and a mean equal to the total exposure divided by the total number of events. This prior will have very little weight but will provide numerical stability to the model. Each factor is incorporated as a proportional hazard rate through an additive linear model of the log-hazard. The default prior for each factor is the same as for the log-odds in the ordinal model. If other non-specified variables are added to the model, then a normal distribution with mean 0 and standard deviation 10 will be utilized.

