5.1 Inclusion Criteria

In order to be eligible to participate in this study, an individual must meet all of the following criteria:

- ≥ 18 years of age
- Hospitalized for COVID-19*
- Enrolled within 72 hours of hospital admittance or 72 hours of positive COVID test
- Expected to require hospitalization for > 72 hours
- See arm-specific Appendices for additional criteria and details

*It is strongly recommended to confirm SARS-CoV2 with a positive PCR or other commercial or public health assay prior to randomization. At centers where there is a delay in confirming the diagnosis, a sufficiently high clinical suspicion is sufficient to proceed with randomization as long as confirmation is expected within 24 hours.

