**9. Duration of hospital stay**

- A time-to-event endpoint of leaving the hospital alive. If a patient is known to leave and return to the hospital within 21 days that intervening time will be ignored.
- This variable will be truncated at 90 days.
- Patients who die in hospital at any time will be considered censored at 90 days.
- Patients still in the hospital at data snapshot will be considered censored at the time of exposure. (at the time the snapshot was taken).

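### SAP 12.4 does not settle the width of the baseline-hazard intervals; if it is 10 days, the hazard ratio for leaving hospital alive can be biased when the discharge hazard changes within an interval

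*SAP*

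**What the plan says.** SAP 12.4 governs every inferential time-to-event analysis. Three of its statements bear on this point:

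- Aim: the model is "intended to mirror a Cox proportional hazards model".
- Baseline: "The underlying hazard will be modeled with a hazard rate for each 10-day period in the model".
- Prior: the next sentence opens "The prior distribution for the hazard rate for each day". It sets a gamma distribution worth one day of exposure, with a mean equal to exposure over events.

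The endpoint most exposed is SAP 7, endpoint 9: "A time-to-event endpoint of leaving the hospital alive". It is truncated at 90 days, and patients who die in hospital are kept without an event to day 90. Endpoint 8 (time to ICU liberation) is built the same way.

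The only fact about early discharge is an inclusion criterion in Protocol 5.1: "Expected to require hospitalization for > 72 hours". The same section allows enrolment within 72 hours of admission or of a positive test.

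SAP 12.7 applies a 99% posterior-probability criterion to each inferential model. Cox regression appears only in SAP 12.8, for post-hoc exploratory work.

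**The concern.** Cox leaves the baseline hazard free. A piecewise model with one hazard per 10 days compares discharges per patient-day within each block, and that ratio equals the hazard ratio only if the hazard is flat there. If few patients go home in the first days after randomization and many do so later in the first block, the early days add patient-time to both arms without adding information, and the effect is diluted. The model-based SD then also differs from the true sampling SD.

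At stake are the reported effect on hospital stay, its credible interval, and the chance that a real shortening of stay meets the 99% criterion. No planned inferential analysis would reveal the problem. The plots in SAP 8 are descriptive. SAP 12.6 allows model changes for poor convergence, but a coarse baseline can converge perfectly well.

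**Working it through.** **No plan figure to reproduce.** The documents give no sample size, event count, hazard ratio or length-of-stay distribution for discharge. From the documents: 10-day or 1-day intervals, truncation at 90 days, 1:1 allocation, deaths held to day 90, 99% criterion (taken here as z > 2.326). Assumed: hazard shapes, median stay, true hazard ratios, 300 patients per arm, and 0% or 7% never discharged.

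**Step 1. Mechanism by hand.** Suppose no control patient leaves for 3 days and the hazard is then constant with median 6 days: ln 2 / 3 = 0.2310 per day. The treated hazard is 1.2 × 0.2310 = 0.2773.

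- Control, days 0-10: discharged 1 − exp(−0.2310 × 7) = 0.8016; patient-days 3 + 0.8016/0.2310 = 6.470; rate 0.1239.
- Treated: discharged 1 − exp(−0.2773 × 7) = 0.8564; patient-days 3 + 0.8564/0.2773 = 6.089; rate 0.1407.

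The first-interval ratio is about 1.135, not 1.20. Later intervals have a constant hazard and give 1.20, so the pooled estimate lies between the two.

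**Step 2. Large-sample limit.** With d and E the expected discharges and patient-days per arm (0, 1) in interval k, the fitted log ratio b solves

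Σk [ d1k − (d0k + d1k) · E1k·e^b / (E0k + E1k·e^b) ] = 0.

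For a true ratio of 1.20 and no deaths:

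| Discharge hazard | Share of discharges in days 0-10 | 10-day intervals |
|---|---|---|
| Weibull shape 2, median 6 d | 88% | 1.138 |
| Lognormal, median 6, sigma 0.6 | 83% | 1.153 |
| Lognormal, median 6, sigma 0.8 | 77% | 1.177 |
| Lognormal, median 8, sigma 0.8 | 64% | 1.184 |
| Lognormal, median 5, sigma 1.0 | 79% | 1.191 |
| Constant, median 5 | 78% | 1.200 |
| Falling (Weibull 0.8, median 6) | 68% | 1.211 |
| Early peak, then decline | 79% | 1.222 |

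One-day intervals give 1.199-1.200 throughout. On the log scale, 1.138 keeps 0.129/0.182 = 71% of the effect and 1.177 keeps 0.163/0.182 = 89%.

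**Step 3. Intervals and power.** Simulation, 300 per arm, true ratio 1.20, no deaths, maximum likelihood standing in for a vague-prior fit:

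| Shape | 10-day ratio | Model SE / empirical SE | 95% coverage | Passes 99%: 10-day | Passes 99%: 1-day |
|---|---|---|---|---|---|
| Weibull 2 | 1.135 | 0.082 / 0.060 | 0.963 | 0.139 | 0.426 |
| Lognormal 0.6 | 1.154 | 0.082 / 0.064 | 0.973 | 0.231 | 0.454 |
| Lognormal 0.8 | 1.179 | 0.082 / 0.074 | 0.965 | 0.351 | 0.464 |
| Constant | 1.202 | 0.082 / 0.084 | 0.946 | 0.468 | 0.466 |
| Weibull 0.8 | 1.210 | 0.082 / 0.086 | 0.939 | 0.476 | 0.434 |

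At a true ratio of 1.0 there is no bias; under lognormal 0.6 coverage is 0.990. At 1.5, coverage falls to 0.811 (lognormal 0.6) and 0.703 (Weibull 2).

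**Step 4. Deaths held to day 90.** With 7% never discharged and a ratio of 1.3 among the rest, the daily fit is the benchmark, because holding deaths at risk lowers the Cox target too. Weibull 2, median 6: 1.110 with 10-day against 1.179 with daily intervals; model SD 0.085 against empirical 0.070; chance of passing 99%, 10% against 36%. Constant hazard: 1.186 against 1.183. Falling: 1.202 against 1.186. With a 14-day median (Weibull 1.5, 7% never discharged, proportional hazards on the subdistribution scale), a true 1.30 gives 1.294.

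**Step 5. The prior limits how the width can be changed.** Take a constant hazard, median 6 and ratio 1.3. Mean stay is 6/ln 2 = 8.66 days (control) and 8.66/1.3 = 6.66 (treated), average 7.66. With 7% held to day 90, exposure is 600 × (0.93 × 7.66 + 0.07 × 90) = about 8,050 days, with 600 × 0.93 = 558 events. Exposure over events is 14.4, which is days per event, not a hazard. Used as a hazard with one day of exposure, it adds 14.4 pseudo-events per interval: 9 × 14.4 = 130 with 10-day intervals and 90 × 14.4 = 1,296 with daily ones, against 558 real events. These load on the baseline, that is the control arm. Simulated ratios as written are 0.78-0.80 (10-day) and 0.20-0.22 (daily), where the prior-free daily fit gives 1.17-1.19. With the mean inverted to 558/8,050 = 0.069 per day, daily intervals still give 1.15-1.17, because 90 × 0.069 = 6.2 pseudo-events remain.

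**The case against.** A reader might infer that the discharge ratio is diluted simply because most discharges fall in one interval. The documents do not support that. They contain no length-of-stay data, and clustering is not the cause: with a constant hazard, 78% of discharges fall in the first interval and the bias is nil. A falling hazard biases away from 1.

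The 72-hour criterion is also weak evidence for a rising hazard. It is an expectation, and the clock starts at randomization, when up to 72 hours in hospital (or more, by the positive-test route) may already have passed. A rising hazard is plausible, not established.

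The daily wording of the prior need not mean daily intervals, since it can be read as a rate per day. So the text is unclear rather than plainly self-contradictory. If daily intervals are meant, the bias disappears.

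The consequences are limited. Under a rising hazard with no true effect the error is conservative, and at a ratio of 1.20 coverage stays near nominal. Protocol 4.2.3 lists length of stay as an additional endpoint, SAP 3.1 does not name it for expedited reports, and no trigger in SAP 4.4 or 12.13 uses it. The moderate P2Y12 arm is retired (Protocol Appendix 8), and the remaining one (Appendix 7) is for severe illness, where stays may be longer.

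All of this stands as a limit on size and certainty. It does not remove the point: the SAP covers both cohorts, applies the 99% criterion to each inferential model, and claims a likeness to Cox that 10-day intervals do not guarantee.

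**Conclusion.** The point holds conditionally. SAP 12.4 leaves the interval width unclear. Read as 10 days, the model does not mirror Cox for discharge when the hazard changes within an interval. If the hazard rises over days 0-10 with a median stay of 5-6 days, a true ratio of 1.20 is estimated as about 1.14-1.18. The model SD is then about 12-38% too large (0.0822/0.0737 to 0.0820/0.0595), and the chance of meeting the 99% criterion falls from 43-46% to 14-35% with 300 per arm. A constant hazard gives essentially no bias, a falling one bias away from 1, and a 14-day median little bias. These sizes rest on assumed shapes and sample size.

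Endpoint 9 is mainly affected, endpoint 8 possibly; no bias has been shown for mortality (endpoint 4). A reader might extend this to the trial's main conclusion, but the organ support-free days analysis is a separate ordinal model, and neither it nor the stopping triggers use the time-to-event model.

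**What to change.** In SAP 12.4, state one interval width. For discharge and ICU liberation, use 1-day intervals to day 28 and wider ones after.

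In the same edit, correct the gamma prior: set its mean to total events divided by total exposure, and scale its exposure to well under one day per interval so that the total prior weight stays negligible. Replacing 10-day with day alone is not safe, because the inverted mean would then be repeated over 90 intervals.

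Alternatively, keep 10-day intervals with the corrected prior mean and pre-specify a Cox or daily-interval sensitivity analysis for endpoints 8 and 9.

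The cost is a short SAP edit, more baseline parameters and a slightly longer run time. No extra data are needed.

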## 4. **Mortality**

- This is a time-to-event endpoint through 90 days.
- Any patient currently in the hospital or transferred on organ support to an alternative care facility will be censored at their last known status alive, regardless of location at the time of that last assessment.
- Any patient successfully discharged from hospital, alive, without organ support, will be censored at the date of discharge if 90-day mortality data are not yet recorded.

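### The baseline-hazard prior for the time-to-event models is the reciprocal of a hazard; coded as written, it would give a null drug a very large false mortality benefit

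*SAP*

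**What the plan says.** SAP section 12.4 governs every inferential time-to-event analysis: "All inferential time-to-event analyses will be done using a Bayesian piecewise exponential model". The baseline is split into pieces: "The underlying hazard will be modeled with a hazard rate for each 10-day period in the model". Each hazard gets a gamma prior worth a single day, whose weight and centre are described as "exposure and a mean equal to the total exposure divided by the total number of events". The section gives its purpose: "This prior will have very little weight but will provide numerical stability to the model".

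Three endpoints in SAP section 7 fall under this rule:

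- mortality (endpoint 4: "This is a time-to-event endpoint through 90 days");
- time to ICU liberation (endpoint 8);
- duration of hospital stay (endpoint 9: "A time-to-event endpoint of leaving the hospital alive").

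Section 12.7 orients all models so that a ratio above 1 is benefit, and treats a posterior probability above 99%, for superiority or inferiority, as significant.

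**The concern.** The parameter is a hazard, in events per patient-day. The stated prior mean is in patient-days per event, so it has the wrong units and is the reciprocal of the intended quantity. When events are uncommon, the gap between a number and its reciprocal is several orders of magnitude.

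The paragraph also contradicts itself. One day of exposure is a negligible weight only if the mean is a small hazard. With a mean of several hundred per day, the same prior contributes several hundred pseudo-events to each piece.

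The harm does not cancel between arms. The prior acts on the baseline hazard, which under reference coding is the control arm's hazard. It inflates that hazard, and the treatment coefficient must then pull the P2Y12 arm back down to its data. The result is a false treatment effect: benefit for death, and harm for a favourable event such as leaving hospital alive.

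**Working it through.** **The prior in explicit form.** A gamma with one day of exposure and mean m is Gamma(shape = m, rate = 1 day). It adds m pseudo-events in one pseudo-day to each piece.

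**Inputs from the documents**

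- 10-day pieces over 90 days, so nine pieces (SAP 12.4; section 7, endpoint 4).
- Treatment prior N(0, 1) on the log scale for a single cohort (SAP 12.1, item 13) or N(0, SD 10) for cohort analyses (SAP 12.5).
- Control effect fixed at 0. Protocol 8.3 states this for the ordinal model; I carry it over.

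**Assumptions, because the documents give no value.** Sample size, 90-day mortality, 1:1 allocation, constant hazard, true hazard ratio 1 and, at first, no covariates.

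**Posterior.** Let d0j, d1j be the deaths and T0j, T1j the exposure in piece j for control and P2Y12. Integrating out the baseline hazards leaves, for the log hazard ratio b,

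p(b) ∝ prior(b) × Π_j exp(b·d1j) / (T0j + T1j·exp(b) + 1)^(d0j + d1j + m).

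I evaluated this on a grid at the expected null counts.

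**Case 1: N = 600, 25% mortality**

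- True hazard: −ln(0.75)/90 = 0.0032 per day. Deaths: 150. Exposure: 150/0.0031965 ≈ 46,927 days.
- Mean as written: 46,927/150 ≈ 313 per day. Pseudo-deaths over nine pieces: 9 × 312.8 ≈ 2,816.
- Hazard ratio for death as written: 0.027 (95% credible interval 0.022–0.034).
- Mean corrected: 150/46,927 = 0.0032 per day, or 0.029 pseudo-deaths in total. Hazard ratio: 1.00 (0.73–1.37).

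**Case 2: N = 1000, 30% mortality**

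- Deaths: 300. Exposure: 75,699 days. Mean as written: 252 per day. Pseudo-deaths: 9 × 252.3 ≈ 2,271.
- Hazard ratio for death as written: 0.063 (0.053–0.074), about 1/0.063 = 16 on the SAP's benefit-above-1 scale. Corrected: 1.00 (0.80–1.25).
- The mechanism shows in the first piece, which has 38.9 deaths and 4,902 days per arm. The fitted control hazard is about (38.9 + 252.3)/(4,902 × 1.063 + 1) = 0.056 per day, 14 times the true 0.0040. The fitted P2Y12 hazard is 0.056 × 0.063 = 0.0035, close to the truth.

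**Range.** For N = 500 to 2000 and mortality 5% to 30%, with either treatment prior, the null hazard ratio for death runs from about 0.001 to 0.118. The posterior probability of benefit is about 1.00 throughout; corrected, it is 0.50. If the prior is applied to each of 90 days instead of nine pieces, the null hazard ratio at N = 1000 is 0.007 or lower.

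**With covariates.** I fitted a reference-coded model with age, sex, history, oxygen, time epoch and 40 sites to 20 simulated null trials per setting (N = 500, 1000, 2000; mortality 10% and 30%; both treatment priors). As written, the median hazard ratio was 0.003 to 0.141, and 20 of 20 trials passed 0.99 for benefit in every setting. Corrected, the medians were 0.79 to 1.04 and 0 of 20 passed.

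**Discharge alive.** Here deaths are carried as non-events to day 90 (SAP section 7, endpoint 9), discharge times are assumed exponential, and N = 1000.

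| Assumed mean stay | Assumed mortality | Prior mean as written | Null HR as written | Null HR corrected |
|---|---|---|---|---|
| 8 days | 10% | 18.0 per day | 0.74 | 1.00 |
| 12 days | 20% | 34.5 per day | 0.56 | 1.00 |
| 12 days | 25% | 42.0 per day | 0.50 | 1.00 |

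The posterior probability of harm is about 1.00 as written in all three rows. In the last row's setting, N = 600 gives 0.38 and N = 300 gives 0.23. I ran no figures for ICU liberation; it uses the same prior, and the direction should be as for discharge.

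**The case against.** **It is probably a slip.** The section says the model should mirror a Cox model and that the prior is nearly weightless. Both are true only of events over exposure, so the intent is clear, and the documents do not show what was programmed. A prior of hundreds of deaths per patient-day might well be noticed. This stands as an account of how the text arose, but the formula remains the operative instruction. Section 12.6 allows noted changes for sampler stability, provided the interpretation is unaffected. It does not mention this prior, and correcting this prior does change the interpretation.

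**No trial decision rests on it.** This is correct. The superiority, futility and inferiority rules use the ordinal model. The four endpoints for expedited reporting in SAP 3.1 are ordinal or dichotomous, and so is 28-day mortality. The DSMB tables use counts and rates. The damage is confined to the three secondary endpoints.

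**Direction and size depend on coding.** This also stands as a condition. In Case 1, coding treatment as ±0.5 gives a null ratio of 1.00 (0.93–1.07), and making P2Y12 the reference gives about 37. In covariate-adjusted null trials (N = 1000, 30% mortality, 10 trials), ±0.5 coding spread the ratio over 0.27 to 2.72; centring every factor held it at 0.95 to 1.06. However, control as reference is the documents' own convention. Protocol 8.3 sets control to zero, SAP 12.4 carries the ordinal model's factor priors over, and the SAP 13.1 output table lists a single P2Y12 term.

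**Conclusion.** The concern holds. The prior mean in SAP 12.4 is the reciprocal of what the parameter requires, it contradicts the section's own description, and nothing elsewhere in the documents corrects it. Coded literally with control as reference, a drug with no effect would show a hazard ratio for death of about 0.03 at N = 600 and 25% mortality, and false harm on discharge. Both cross the SAP's 99% line. Sample size, mortality, length of stay and hazard shape are assumptions. They change the size of the error, but the false mortality signal appears at every setting tried under reference coding. The primary analysis is unaffected. The point should still be fixed before analysis, because it governs the inferential 90-day mortality result, and programmers following the words and the intent would reach irreconcilable answers.

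**What to change.** In SAP 12.4, define the prior for each 10-day hazard piece as a gamma distribution with one day of exposure and a mean equal to total events divided by total exposure. This also settles the section's switch from 10-day periods to single days. State that control is the reference level in these models. Check that the analysis code uses the corrected ratio. The cost is a sentence or two of wording and a code check; there is no statistical downside, and no effect on sample size or on the interim rules.
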